17.2. DEATHS

If any subject dies during the study as recorded on the adverse events page of the eCRF, the information will be presented in a data listing.

17.3. LABORATORY EVALUATIONS

Local laboratory results will be included in the reporting of this study for Hematology, Blood Chemistry

Document:	L:\BIOS\Boehringer_Ingelheim_Pharmaceuticals\BI730357\1407-0037_MZA56588\Biostatistics\Documentation\SAP		
Author:	[REDACTED]	Version Number:	Final V2.0

Template No: CS_TP_BS016 – Revision 5
Effective Date: 01Apr2018

Reference: CS_WI_BS005

and Urinalysis. A list of laboratory assessments to be included in the outputs is included in APPENDIX 3. Presentations will use System International (SI) Units, as provided by the labs.

Protocol-specified clinical laboratory tests will be summarized using descriptive statistics. Clinical laboratory data collected during study conduct, which were not required per protocol, such as for special testing to evaluate an AE, will be listed separately and not summarized.

Quantitative laboratory measurements reported as “ $< X$ ”, i.e. below the lower limit of quantification (BLQ), or “ $> X$ ”, i.e. above the upper limit of quantification (ULQ), will be converted to X for the purpose of quantitative summaries, but will be presented as recorded, i.e. as “ $< X$ ” or “ $> X$ ” in the listings.

All available data will be listed.

The following summaries by treatment will be provided for laboratory data:

- Actual and change from baseline by visit (for quantitative measurements)
- Incidence of as abnormal values according to normal range criteria for urinalysis
- Incidence of Drug-Induced Liver Injury (DILI) findings
- Listing of lab results outside the normal range.

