7.2.5 Safety analyses

Adverse events will be coded using the Medical Dictionary for Drug Regulatory Activities (MedDRA). Standard BI summary tables and listings will be produced. All adverse events with an onset between start of treatment and end of the REP, a period of 7 days after the last dose of trial medication, will be assigned to the on-treatment period for evaluation.

The safety analysis will be done by 'randomised treatment'.

All treated subjects will be included in the safety analysis. In general, safety analyses will be descriptive in nature and will be based on BI standards. No hypothesis testing is planned.

Statistical analysis and reporting of adverse events will concentrate on treatment-emergent adverse events, i.e. all adverse events occurring between start of treatment and end of the REP. Adverse events that start before first drug intake and deteriorate under treatment will also be considered as 'treatment-emergent'.

Frequency, severity, and causal relationship of adverse events will be tabulated by system organ class and preferred term after coding according to the current version of the Medical Dictionary for Drug Regulatory Activities (MedDRA) at database lock.

c27983101-03 Clinical Trial Protocol Page 66 of 79

Proprietary confidential information © 2020 Boehringer Ingelheim International GmbH or one or more of its affiliated companies

Laboratory data will be analysed both quantitatively as well as qualitatively. The latter will be done via comparison of laboratory data to their reference ranges. Values outside the reference range as well as values defined as clinically relevant will be summarised. Treatment groups will be compared descriptively with regard to distribution parameters as well as with regard to frequency and percentage of subjects with abnormal values or clinically relevant abnormal values.

Vital signs, physical examinations, or other safety-relevant data observed at screening, baseline, during the course of the trial and at the end-of-trial evaluation will be assessed with regard to possible changes compared to findings before start of treatment.

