17.6. PHYSICAL EXAMINATION

The results of physical examination will be only be included in the source documents available at the site.

Document:	L:\BIOS\Boehringer_Ingelheim_Pharmaceuticals\BI730357\1407-0037_MZA56588\Biostatistics\Documentation\SAP		
Author:	██████████	Version Number:	Final V2.0
	Version Date: 23JUL2020		
Template No:	CS_TP_BS016 – Revision 5		
Effective Date:	01Apr2018		
	Reference: CS_WI_BS005		
Copyright © 2009, 2010, 2012, 2016, 2018 █████ All Rights Reserved. The contents of this document are confidential and proprietary to █████ and its subsidiaries. Unauthorized use, disclosure or reproduction is strictly prohibited.			

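### Apart from the DILI table, the SAP specifies abnormal-value frequencies for urinalysis only, although the protocol promises them by treatment group for all laboratory data

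*SAP*

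**What the plan says.** **Protocol 7.2.5 (Safety analyses)** plans both a quantitative and a qualitative analysis of laboratory data. On the qualitative side, "Values outside the reference range as well as values defined as clinically relevant will be summarised", and groups are compared descriptively on the "frequency and percentage of subjects with abnormal values or clinically relevant abnormal values". No laboratory group is singled out or excepted. The same section covers physical examination, which, like the other safety data it names, "will be assessed with regard to possible changes compared to findings before start of treatment".

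**SAP 17.3 (Laboratory evaluations)** names four outputs by treatment:
- actual values and changes from baseline by visit, for quantitative tests;
- one reference-range table, worded as "Incidence of as abnormal values according to normal range criteria for urinalysis";
- a liver table, worded as "Incidence of Drug-Induced Liver Injury (DILI) findings";
- for everything else out of range, a "Listing of lab results outside the normal range".

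**SAP 17.3.2** classifies every quantitative laboratory result as Low, Normal or High against the reference range.

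**SAP 17.6** says of physical examination: "The results of physical examination will be only be included in the source documents available at the site". SAP 2.3 still names physical examination among the bases for the safety objectives.

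**SAP 3.3** is the place for departures from the protocol. Its legible text covers a dropped further objective and the renaming of the index, and nothing on laboratory data or physical examination.

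**The concern.** SAP Section 1 says the plan rests on the analysis specified in Section 7 of the protocol, and 7.2.5 belongs to that section. A comparison promised there should therefore either appear in the SAP or be recorded as dropped. For haematology and general chemistry neither has happened.

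The comparison is relevant to this trial. Protocol 1.4.2 names infection through impaired host defence as a theoretical risk of BI 730357. It also lists leukopenia and aminotransferase elevations among the laboratory changes seen with ciprofloxacin. Neutrophils, lymphocytes, ALT and AST are measured on treatment and at end of trial (Protocol Table 5.2.3: 1). At stake is a simple descriptive answer: how many subjects in each arm went out of range on these tests.

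**Working it through.** The plan states no figure to reproduce here. The check sets the two documents side by side and then traces what happens to each kind of abnormal result.

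**Step 1. Promise against specified output**

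| Item | Protocol 7.2.5 | SAP |
|---|---|---|
| Subjects outside reference range, haematology and general chemistry | Frequency and percentage by group | No frequency table; listing only (17.3) |
| Subjects outside reference range, urinalysis | Frequency and percentage by group | Incidence table (17.3) |
| Marked AST, ALT and bilirubin elevation | Covered by the general promise | DILI incidence table (17.3, 17.3.1) |
| Clinically relevant laboratory values | Frequency and percentage by group | No laboratory table; reach the adverse event tables through Protocol 5.2.3 |
| Physical examination | Assessed for change from before treatment | Source documents only (17.6) |

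The Low/Normal/High categories in SAP 17.3.2 feed no specified table. SAP 6.6 mentions shift tables only as a general example, and 17.3 lists none for laboratory data.

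**Step 2. Where each abnormal result is counted**

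- *Judged clinically relevant by the investigator.* Reported as an adverse event (Protocol 5.2.3). If treatment-emergent, it is counted by system organ class, preferred term and treatment (SAP 17.1), though not by laboratory parameter.
- *Meets DILI criteria.* Counted by treatment. The criteria in SAP 17.3.1 are AST and/or ALT at least 3 times the upper limit of normal (ULN) together with total bilirubin at least 2 times ULN, or AST and/or ALT at least 10 times ULN.
- *Neither of these.* Not counted by arm. An ALT from 3 to just under 10 times ULN with bilirubin below 2 times ULN falls here unless it is reported as an adverse event. So do all out-of-range neutrophil and lymphocyte counts that are not reported as adverse events.

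**Step 3. What the remaining outputs show for that last group**

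SAP 6.1 gives n, mean, SD, median, IQR, minimum and maximum for quantitative variables. The minimum or maximum reveals the single most extreme value in an arm. It does not say whether one subject or several were out of range, because the same minimum fits both. The listing contains all of them, but the reader would have to count by hand.

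**Step 4. Which tests are affected**

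Protocol Table 5.2.3: 1 schedules haematology with differential, AST, ALT, AP, GGT, glucose, creatinine, urea nitrogen, uric acid and bilirubin on Day 8 and at end of trial. Lipase, amylase and electrolytes are scheduled after baseline only at end of trial. Creatine kinase, albumin, CRP, total cholesterol and coagulation are scheduled only at screening, so no planned post-baseline count can be made for them.

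**Step 5. Scale**

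Protocol 3.2 plans 27 subjects on active drug in each dose group. As an illustration, if two or three subjects in one arm went out of range:

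- 2/27 = 7.4%
- 3/27 = 11.1%

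These counts are assumed, not predicted. They show the size of difference that would have no tabulated frequency.

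**The case against.** The strongest reply is that most of what matters is already counted. Marked liver abnormalities have their own table. Findings the investigator considers clinically relevant become adverse events and are tabulated by treatment. Severe, opportunistic and tuberculosis infections have separate summaries (SAP 17.1.3). The quantitative tables carry minimum and maximum. Safety is descriptive, with no hypothesis test. SAP Section 8 also refers to templates that set the content of the tables, and those are not among the documents.

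Much of this stands, and it rules out several stronger readings:

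- *A reader might infer that chemistry abnormalities appear in no table.* The DILI table contradicts that.
- *A reader might infer that only means are shown, or that extremes are hidden.* SAP 6.1 contradicts that.
- *A reader might infer that clinically relevant laboratory values go uncounted.* The adverse event route contradicts that, although it gives no count by parameter.
- *A reader might infer that physical examination findings drop out of the analysis altogether.* Protocol 5.2.1 itself directs results to the source documents, so SAP 17.6 follows one part of the protocol while departing from 7.2.5. Clinically relevant changes are recorded as adverse events (Protocol 5.2.6.1.1), and the irradiated skin sites have their own grading (Protocol 5.1). This is a tension within the protocol plus a missing note in the SAP.

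The reply does not remove the main discrepancy. Protocol 7.2.5 asks for abnormal values as well as clinically relevant ones, and the adverse event route supplies only the latter. An unseen template might contain the missing table, but the SAP text, which is the specification, names none.

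**Conclusion.** The concern holds in a limited form. Protocol 7.2.5 commits to abnormal-value frequencies by treatment group for all laboratory data. Apart from DILI, SAP 17.3 specifies them for urinalysis only, and SAP 3.3 does not declare the difference. The gap covers haematology and general chemistry values measured after baseline that are out of range, not reported as adverse events and below the DILI criteria. Those values are listed, and their extremes are visible, but the number of subjects affected in each arm is not given.

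This affects a protocol-specified descriptive safety comparison and has no bearing on the primary photosensitivity result. The change should be made, but it is a matter of completeness and traceability. The conclusion assumes that the unseen templates add no such table and that the redacted words in SAP 3.3 do not declare the change. The legible sentence around that redaction concerns a further objective.

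**What to change.** **SAP 17.3.** Add, by treatment, the number and percentage of subjects with a post-baseline Low and a post-baseline High value for each haematology and chemistry test measured after baseline. Use the categories in SAP 17.3.2 and the safety columns in SAP 17: pooled placebo, each BI 730357 dose, pooled BI 730357, and ciprofloxacin. A baseline-to-worst shift layout is optional. It would separate new abnormalities from those already present, but the protocol asks only for frequencies.

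**Clinically relevant values.** State in 17.3 that these are taken from the adverse event tables. The documents describe no separate database flag for them, so a dedicated laboratory table might need new data capture and is not requested.

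**Physical examination.** Reconcile SAP 17.6 with SAP 2.3 and Protocol 7.2.5 by a note in SAP 3.3 that results stay in source documents and clinically relevant changes are analysed as adverse events. A listing of findings is not requested, because the documents do not place those results in the database.

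**Cost.** One additional set of standard tables, built on a categorisation that is already planned, and a short entry in SAP 3.3. No new measurement is needed.

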17.3.1. DRUG INDUCED LIVER INJURY (DILI)

- Normal liver function at Baseline is defined as AST, ALT and total bilirubin values measured at baseline are each \leq the respective ULN
- For post baseline visits:
 - Subjects with normal liver function at baseline and AST and/or ALT ≥ 3 times ULN combined with total bilirubin ≥ 2 times ULN measured in the same blood draw sample
 - AST and/or ALT ≥ 10 times ULN.

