3.3.3 Exclusion criteria

- 1. Any finding in the medical examination (including blood pressure, pulse rate or ECG) deviating from normal and judged as clinically relevant by the Investigator.
- 2. Any laboratory value outside the reference range that the Investigator considers to be of clinical relevance.
- 3. Gastrointestinal, hepatic, renal, respiratory, cardiovascular, metabolic, immunological or hormonal disorders or any evidence of a concomitant disease judged as clinically relevant by the Investigator.
- 4. Major surgery (major according to the investigator's assessment) performed within 10 weeks prior to randomisation or planned within 2 months after screening.
- 5. Any documented active or suspected malignancy or history of malignancy within 5 years prior to screening, except appropriately treated basal cell carcinoma of the skin or in situ carcinoma of uterine cervix.
- 6. Active skin disorders on the back where photosensitivity testing will be performed.
- 7. Subjects who must or wish to continue the intake of restricted medications (see section 4.2.2.1) or any drug considered likely to interfere with the safe conduct of the trial.
- 8. Subjects not expected to comply with the protocol requirements or not expected to complete the trial as scheduled (e.g. chronic alcohol or drug abuse or any other condition that, in the investigator's opinion, makes the subject an unreliable trial participant).
- 9. Currently enrolled in another investigational device or drug trial, or less than 30 days (or 5 half-lives (whichever longer)) since ending another investigational drug trial.
- 10. Women who are pregnant, nursing, or who plan to become pregnant while in the trial.
- 11. History of relevant allergy or hypersensitivity (including allergy to the trial medication or its excipients).
- 12. History of hypersensitivity to ciprofloxacin, any member of the quinolone class of antibacterials.
- 13. History of hypersensitivity to sunlight or artificial source of intense light, especially UV light.
- 14. Chronic or acute infections which are of relevance in the opinion of the Investigator.
- 15. Positive result for HIV, HBV, and hepatitis C (Hep C) at screening.
- 16. History of TB or positive finding in IGRA.
- 17. Unwillingness/inability to refrain from intake of alcoholic beverages from 48 hours prior to the trial medication administration and until Day 7 post trial medication administration.
- 18. Positive drug screening.

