5.2.6.1.4 Adverse events of special interest

The term adverse events of special interest (AESI) relates to any specific AE that has been identified at the project level as being of particular concern for prospective safety monitoring and safety assessment within this trial, e.g. the potential for AEs based on knowledge from other compounds in the same class. AESIs need to be reported to the sponsor's Pharmacovigilance Department within the same timeframe that applies to SAEs, please see section 5.2.6.2.2.

The following are considered as AESIs:

Hepatic injury

A hepatic injury is defined by the following alterations of hepatic laboratory parameters:

- an elevation of AST (Aspartate Aminotransferase) and/or ALT (Alanine Aminotransferase) ≥3 fold ULN combined with an elevation of total bilirubin ≥2 fold ULN measured in the same blood draw sample, or
- Aminotransferase (ALT, and/or AST) elevations ≥10 fold ULN.

These lab findings constitute a hepatic injury alert and the subjects showing these lab abnormalities need to be followed up according to the "DILI checklist" provided in the ISF.

In case of clinical symptoms of hepatic injury (icterus, unexplained encephalopathy, unexplained coagulopathy, right upper quadrant abdominal pain, etc.) without lab results (ALT, AST, total bilirubin) available, the investigator should make sure these parameters are analysed, if necessary in an unscheduled blood test. Should the results meet the criteria of hepatic injury alert, the procedures described in the DILI checklist should be followed.

c27983101-03 Clinical Trial Protocol Page 54 of 79

Proprietary confidential information © 2020 Boehringer Ingelheim International GmbH or one or more of its affiliated companies

Severe infections (according to RCTC grading)

Opportunistic and mycobacterium tuberculosis infections

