17.1.3. ADVERSE EVENTS OF SPECIAL INTEREST

The following AEs will be recorded as Adverse Events of Special Interest (AESIs) in this trial:

Hepatic Injury

Hepatic injury defined by the following alterations of liver parameters (for subjects with normal liver function at baseline):

- An elevation of aspartate aminotransferase (AST) and/or alanine aminotransferase (ALT) ≥ 3 times the upper limit of normal (ULN) combined with an elevation of bilirubin ≥ 2 times ULN measured in the same blood draw sample;

Document: L:\BIOS\Boehringer_Ingelheim_Pharmaceuticals\BI730357\1407-0037_MZA56588\Biostatistics\Documentation\SAP

Author: [REDACTED] Version Number: Final V2.0
Version Date: 23JUL2020

Template No: CS_TP_BS016 – Revision 5
Effective Date: 01Apr2018

Reference: CS_WI_BS005

- Aminotransferase (ALT, and/or AST) elevations ≥ 10 fold ULN.

Severe infections

Opportunistic and mycobacterium tuberculosis infections

These include pneumocystis jirovecii, BK virus disease including PVAN, CMV, posttransplant lymphoproliferative disorder (EBV), progressive multifocal leucoencephalopathy, bartonellosis (disseminated only), blastomycosis, toxoplasmosis, coccidioidomycosis, histoplasmosis, aspergillosis (invasive only), candidiasis (invasive or pharyngeal), cryptococcosis, other invasive fungi (mucormycosis (zygomycosis, rhizopus, mucor, lichtheimia), scedosporium/pseudallescheria boydii, fusarium), legionellosis, listeria monocytogenes (invasive only), tuberculosis, nocardiosis, non-tuberculous mycobacterium, salmonellosis (invasive only), HBV reactivation, herpes simplex (invasive only), herpes zoster, strongyloides (hyperinfection syndrome and disseminated forms only), paracoccidioides, penicillium marneffei, sporothrix schenckii, cryptosporidium species (chronic only), microsporidiosis, leishmaniasis (visceral only), trypanosoma cruzi infection (Chagas' disease) (disseminated only), campylobacteriosis (invasive only), shigellosis (invasive only), vibriosis (invasive due to vibrio vulnificus), HCV progression.

The AESIs are those TEAEs with YES response to the question, "Adverse Event of Special Interest? "on the AE page of the eCRF and will be flagged in listing.

Incidence summaries by SOC and PT will be prepared for each treatment for the following:

- All AEs of hepatic injury
- All AEs of hepatic injury by severity
- All severe infections according to RCTC grading
- All opportunistic and mycobacterium tuberculosis infections

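### The SAP's DILI table limits the combined aminotransferase-bilirubin criterion to subjects with normal baseline liver tests, a condition the protocol's hepatic injury definition does not contain

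*SAP*

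**What the plan says.** **Protocol 5.2.6.1.4 (Adverse events of special interest).** The definition opens "A hepatic injury is defined by the following alterations of hepatic laboratory parameters" and gives two criteria. The first is "an elevation of AST (Aspartate Aminotransferase) and/or ALT (Alanine Aminotransferase) ≥3 fold ULN combined with an elevation of total bilirubin ≥2 fold ULN", both measured in one blood sample. The second is "Aminotransferase (ALT, and/or AST) elevations ≥10 fold ULN". Neither depends on the subject's baseline values. The section continues "These lab findings constitute a hepatic injury alert" and sends the subject to follow-up under the DILI checklist.

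**SAP 17.3 and 17.3.1.** Section 17.3 plans a by-treatment incidence summary of DILI findings, and 17.3.1 supplies its only definition. It first sets a baseline rule, "Normal liver function at Baseline is defined as AST, ALT and total bilirubin values measured at baseline are each" at or below the respective ULN. The combined criterion then begins "Subjects with normal liver function at baseline and AST and/or ALT". The 10-fold criterion is a separate bullet with no baseline condition.

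**SAP 17.1.3.** The lead-in reads "Hepatic injury defined by the following alterations of liver parameters (for subjects with normal liver function at baseline" and stands above both criteria. Later in the same section, AESIs are selected by a yes answer on the adverse event page of the eCRF.

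**SAP 3.3 (Changes to analysis from protocol).** The entries are a dropped further objective and the renaming of the index. The liver criterion is not mentioned.

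**Protocol 3.3.3, exclusion criterion 2.** The exclusion applies to "Any laboratory value outside the reference range that the Investigator considers to be of clinical relevance". An out-of-range value judged not relevant does not exclude.

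**The concern.** The protocol and the SAP use the same thresholds for the same kind of event but count it in different subjects. Drug-induced liver injury is the first entry in the protocol's risk table (1.4.2). Among the laboratory summaries in SAP 17.3, the DILI table is the only incidence table computed from blood liver tests; the abnormal-value incidence summary there covers urinalysis. It should therefore serve as a check, independent of the investigator's AESI flag, on whether any subject met the protocol's alert.

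With the baseline condition in place, it cannot do this for a subject who starts above ULN. The site would apply the unrestricted protocol rule and could report a hepatic injury AESI while the DILI table shows no finding for that subject. A reader of the report would have no stated reason for the difference.

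**Working it through.** No power, alpha or sample size enters here, and the plan states no figure to reproduce. The check compares the rules as logical conditions.

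**Notation.** B = AST, ALT and total bilirubin all at or below ULN at baseline (SAP 17.3.1). T = the higher of AST and ALT after baseline, in multiples of ULN. L = total bilirubin in the same sample, in multiples of ULN.

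**Rules.**
- Protocol 5.2.6.1.4: (T ≥ 3 and L ≥ 2) or T ≥ 10.
- SAP 17.3.1: (B and T ≥ 3 and L ≥ 2) or T ≥ 10.
- SAP 17.1.3 as worded: B and [(T ≥ 3 and L ≥ 2) or T ≥ 10].

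**Comparison** over two baseline states, T = 2, 5, 12 and L = 1, 2.5 (2 × 3 × 2 = 12 cells):

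| Baseline | T | L | Protocol | SAP 17.3.1 | SAP 17.1.3 wording |
|---|---|---|---|---|---|
| normal | 2 | 1 | no | no | no |
| normal | 2 | 2.5 | no | no | no |
| normal | 5 | 1 | no | no | no |
| normal | 5 | 2.5 | yes | yes | yes |
| normal | 12 | 1 | yes | yes | yes |
| normal | 12 | 2.5 | yes | yes | yes |
| above ULN | 2 | 1 | no | no | no |
| above ULN | 2 | 2.5 | no | no | no |
| above ULN | 5 | 1 | no | no | no |
| above ULN | 5 | 2.5 | **yes** | **no** | **no** |
| above ULN | 12 | 1 | yes | yes | **no** |
| above ULN | 12 | 2.5 | yes | yes | **no** |

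SAP 17.3.1 differs from the protocol in 1 of 12 cells, and the 17.1.3 wording differs in 3 of 12. The cells are illustrative patterns, not frequencies. In general, the protocol rule is met and the 17.3.1 rule is not exactly when B is false, 3 ≤ T < 10 and L ≥ 2.

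**Can B be false in a treated subject?** Yes. Exclusion criterion 2 leaves room for a value above ULN that the investigator considers not relevant. SAP 6.5 takes baseline as the last scheduled pre-dose value, generally Day -1 or Day 1 for safety assessments, so a subject normal at screening can also be above ULN at baseline.

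**Where would the subject still be seen?** SAP 17.3 lists all laboratory data and separately lists out-of-range results. The AESI tables in 17.1.3 follow the eCRF answer, so an event flagged by the investigator appears there whatever the baseline value. Only the DILI incidence table omits the subject.

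**After the fix.** Without B, the 17.3.1 rule is (T ≥ 3 and L ≥ 2) or T ≥ 10. This is the protocol rule, and the discordant cell disappears.

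**The case against.** The strongest reply has four parts.

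- *Nothing is hidden.* The protocol alert works for any subject, AESIs go to the sponsor within 24 hours (5.2.6.2.2), the AESI tables follow the eCRF flag, and the laboratory data are listed. This stands. A reader might infer that a liver signal would be lost; the documents do not support that.
- *The parenthesis in SAP 17.1.3 changes no result.* This also stands. A reader might infer that the AESI tables drop subjects with abnormal baseline for both criteria, but those tables are driven by the eCRF answer. The disagreement between 17.1.3 and 17.3.1 on the 10-fold rule is one of wording, and 17.3.1 leaves that rule unrestricted.
- *The DILI table is the SAP's own addition.* Protocol 7.2.5 does not plan it, and restricting a criterion to subjects normal at baseline is a recognisable way to describe new abnormality. This stands in part. The SAP gives no reason for the restriction, applies it to one criterion and not the other, and takes its thresholds from the protocol definition, so a reader would expect the two counts to match.
- *The situation is unlikely.* Subjects are healthy volunteers screened by laboratory tests, dosing of BI 730357 or placebo lasts 8 days, scheduled liver tests after dosing fall only on Day 8 and at the end-of-treatment visit, and safety analysis is descriptive. This stands and limits the importance of the point, but it does not make the rule right.

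**Conclusion.** The point holds in a narrow form. Followed as written, SAP 17.3.1 gives a wrong count, measured against protocol 5.2.6.1.4, for a subject with AST, ALT or total bilirubin above ULN at baseline who then reaches AST/ALT of at least 3x and below 10x ULN with total bilirubin at least 2x ULN in the same sample. The effect is confined to the DILI incidence table, which could then disagree with the AESI tables. No photosensitivity endpoint and no safety action at the site depends on it.

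No number of affected subjects can be given. A reader might try to derive one by treating ULN as a fixed percentile and the three tests as independent. The documents support neither assumption and give no rate of baseline elevation, and the result would count subjects outside the criterion, not events omitted from the table. Omitted events should be very rare. The conclusion rests on the wording of the two definitions and on exclusion criterion 2 being applied as written.

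**What to change.** In SAP 17.3.1, delete the baseline condition from the bullet that begins "Subjects with normal liver function at baseline and AST and/or ALT", so that it starts at the aminotransferase threshold and the DILI table uses the protocol's definition for all treated subjects. If baseline status is of interest, keep the definition of normal baseline and show baseline-normal and baseline-abnormal subjects as sub-rows. Remove the matching parenthesis from the lead-in of SAP 17.1.3, so that protocol 5.2.6.1.4 and both SAP sections read alike; this leaves the AESI tables unchanged.

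If the restriction is intended, state it with its reason in SAP 3.3, make 17.1.3 and 17.3.1 agree, and show the unrestricted count beside the restricted one.

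The cost is two phrases in the SAP and one line of table code, with no extra data.
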